13.7.2 Secondary Efficacy Analysis

A comparison of part I (unenhanced MRI alone) and part III (mangoral-enhanced MRI alone) will be analyzed in the same way as the primary endpoint.

All other efficacy variables specified in [Section 9.2.3](#) (and listed in [Table 1](#)) will be analyzed using descriptive statistics (including 2-sided 95% confidence intervals) for the full analysis population (FAS) and the per protocol set (PPS).

For each reader, the percentage of patients who had improvement in at least one co-primary variable for at least one lesion on part II (CMRI) and part III (mangoral-enhanced MRI alone) compared to part I (unenhanced MRI) will be calculated. In addition, the percentage of patients who had improvement in both BD and LC for at least one lesion on part II (CMRI) and part III (mangoral-enhanced MRI alone) compared to part I (unenhanced MRI) will be calculated. Similarly, there will be also calculated percentage of patients who had at least one new lesion identified on part II (CMRI) and part III (mangoral-enhanced MRI alone) compared to part I (unenhanced MRI).

Additionally, assuming repeated assessments per patient (for approximately 20 patients) by three independent readers, an intra-reader reproducibility will be evaluated separately for readings of MRIs in parts I, II and III. Based on a patient-level approach, the intra-reader and inter-reader variability will be analyzed using linear mixed-effects models fitted to individual mean scores of border delineation (BD) and lesion contrast (LC). Basically, the model will include reader, patient and replicate as a random effects and divide the total variability into an intra- and inter-reader component, in case this model does not converge we will have patient as a fixed effect instead.

Considering reader as a random effect, this model is used to express the observed value as the true value plus the intra-reader error with inter-reader variance $\sigma_B^2 = \text{var}(\mu_i)$ and intra-reader variance $\sigma_W^2 = \text{var}(e_{ik})$. As a relative measure of reproducibility, the intra-reader coefficient of variation (wCV) defined as $wCV = \sigma_W / \mu$ where $\mu = E(\mu_i)$ is taken as the mean of true value. The Intraclass Correlation Coefficient (ICC) will also be derived as the inter-reader variability divided by the total variability.

Bland–Altman plots [\[4\]](#) (showing differences versus mean, with mean difference and 95% limits of agreement) will be used for graphical presentations of intra- and inter-reader agreements for part I (unenhanced MRI) versus part II (CMRI) and part I (unenhanced MRI) versus part III (mangoral-enhanced MRI alone) as well.

For inter-reader plots, separate plots will be shown for BD and LC. For each MRI type, plots will be done for each pairwise comparison: reader 2 vs. reader 1, reader 3 vs. reader 1 and reader 3 vs. reader 2.

For a number of patients BD and LC will be assessed twice by each reader and MRI type. For intra-reader plots, separate plots will be shown for BL and LC, for each reader and MRI type plots will be done against first vs. second read (for those matched lesions).

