#### **Inter-reader and intra-reader agreement:**

Additionally, assuming repeated assessments per subject by three independent readers, an intra-reader and inter-reader reproducibility will be evaluated separately for MRI readings in Parts I, II and III using linear mixed-effects models fitted to individual mean scores of border delineation (BD) and lesion contrast (LC), considering patients as a random effect. Details of the statistical model will be specified in the SAP.

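### The reproducibility model names no reader-by-patient term, so on its plain reading the intra-reader variance and wCV overstate re-read error whenever readers disagree patient by patient

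*SAP*

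**What the plan says.** Protocol 8.1.4 promises that "an intra-reader and inter-reader reproducibility will be evaluated separately for MRI readings in Parts I, II and III". It specifies patient as a random effect and leaves the rest of the model to the SAP.

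SAP 13.7.2 supplies the model, fitted to each patient's mean BD and LC score:

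- **Effects:** "the model will include reader, patient and replicate as a random effects and divide the total variability into an intra- and inter-reader component".
- **Fallback:** "in case this model does not converge we will have patient as a fixed effect instead".
- **Decomposition:** "this model is used to express the observed value as the true value plus the intra-reader error with inter-reader variance" var(μ_i) and intra-reader variance var(e_ik). The indices are not defined.
- **Summary measure:** "As a relative measure of reproducibility, the intra-reader coefficient of variation (wCV) defined as" σ_W/μ.
- **Data:** "assuming repeated assessments per patient (for approximately 20 patients) by three independent readers", and "For a number of patients BD and LC will be assessed twice by each reader and MRI type".

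The same section plans intra-reader Bland–Altman plots of first against second read, by reader and MRI type. Neither document mentions a reader-by-patient effect.

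**The concern.** Intra-reader error should mean how far one reader's second score for a patient departs from the same reader's first score. Readers can differ from each other in two ways. One reader may be more lenient throughout, which the reader effect captures. Readers may also differ on particular patients, one scoring patient A higher and another scoring patient B higher. The second kind needs a reader-by-patient effect. Without it the model has only the residual in which to put that variation, and the residual is what gets reported as intra-reader.

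Some variation of the second kind is to be expected. Each reader detects lesions independently (SAP 9.2.1), and the patient's score is built reader by reader from the lesions that reader scored (SAP 11.2.2). Two readers can therefore average over different lesions in the same patient.

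What is at stake is the labelling of a descriptive result. Readers who repeat themselves well but differ from one another would be tabulated as poor at repeating themselves, and the inter-reader component would leave out patient-specific disagreement.

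**Working it through.** The documents state no variance component, wCV or ICC, so there is no planned figure to reproduce. The check is what the stated model estimates.

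**Inputs from SAP 13.7.2.** P = 20 re-read patients (approximate), R = 3 readers, K = 2 reads per reader and MRI type; main effects for reader, patient and replicate.

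**Assumed.** s_e² is the true re-read variance and s_RP² the reader-by-patient variance. Neither is in the documents, so the ratio q = s_RP²/s_e² is varied from 0 to 2.

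**Degrees of freedom for one MRI part.**
- Reads: 20 × 3 × 2 = 120, so 119 df in total.
- Main effects: 19 (patient) + 2 (reader) + 1 (replicate) = 22.
- Residual: 119 − 22 = 97. Of these, (20 − 1)(3 − 1) = 38 carry the interaction and 20 × 3 − 1 = 59 are pure re-read error.

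**Expected residual variance.**

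[38(s_e² + 2 s_RP²) + 59 s_e²]/97 = s_e² + (76/97) s_RP² = s_e² + 0.78 s_RP²

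The weight hardly depends on the approximate 20: it is 0.778 with 15 patients and 0.787 with 25.

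**Overstatement of σ_W and wCV** = √(1 + 0.7835 q):

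| Assumed q | Factor |
|---|---|
| 0 | 1.00 |
| 0.25 | 1.09 |
| 0.5 | 1.18 |
| 1 | 1.34 |
| 2 | 1.60 |

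**Simulation check.** With true s_e² = s_RP² = 0.090 (assumed), theory gives a residual of 0.090 × 1.7835 = 0.1605. Over 2,000 simulated data sets the mean residual was 0.159 without the interaction term and 0.0897 with it. Fifteen REML fits averaged 0.163 and 0.093.

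**Fallback.** Making patient a fixed effect leaves the same 97 residual df with the same content, so it does not help.

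**If single-read patients were also fitted.** With 20 patients read twice and the rest once, the weight on s_RP² is 0.886 for 59 patients in total (the evaluable number in SAP 9.3) and 0.909 for 80. At q = 1 the factors are √1.886 = 1.37 and √1.909 = 1.38. The SAP introduces the evaluation for the repeated assessments, so this is a side case.

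**Can the missing term be estimated?** Yes. The planned re-reads give 38 df for the interaction and 59 for pure error.

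**The case against.** **The wording is loose.** The SAP does not call the model additive, does not define i and k, and does not say how replicate is nested. If i denoted a reader–patient cell and k the read, e_ik would be pure re-read error. That stands as a reason for a conditional conclusion, but it does not remove the point. On that reading var(μ_i) would contain patient variance and could not be called inter-reader. Nesting replicate within reader-by-patient makes it coincide with the residual and separates nothing.

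**Re-read error is already displayed.** In the intra-reader Bland–Altman plots reader-by-patient variation cancels, because each difference is within one reader and patient. A stable reader will look stable there. This is a real safeguard, but a partial one: the plots yield no tabulated σ_W or wCV, may be drawn by lesion, and could visibly disagree with the tabulated wCV.

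**Nothing depends on it.** A reader might infer that intra-reader error is the yardstick for the treatment effect, or that trial success is affected. The documents do not support either. Success rests on paired t-tests of Diff(BD) and Diff(LC) for each reader, in two of three readers (SAP 13.7.1). Neither σ_W nor wCV enters those tests or the sample size, no acceptance limit is set for wCV, and SAP 10.2 makes all tests outside the primary analysis exploratory.

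**The direction is unfavourable to the readers.** For re-read error the bias makes reading look less repeatable, so it cannot give false reassurance on that quantity. This also stands.

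**Conclusion.** The point holds conditionally. On the plain reading of SAP 13.7.2 the reported intra-reader variance is s_e² + 0.78 s_RP², so σ_W and wCV exceed a reader's own re-read error whenever s_RP² is above zero. The factors of 1.00 to 1.60 rest wholly on the assumed variance ratios.

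It would go too far to say that the reported figures will be wrong by a known amount. There is no bias if s_RP² is zero, the factor is only 1.09 at a ratio of 0.25, and the documents give no basis for choosing a ratio. A reader's average shift is not part of the problem, since the reader term takes it up. This is a low-priority correction to a descriptive result, with no bearing on the primary conclusion.

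**What to change.** In SAP 13.7.2, separately for each MRI part:

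1. Add a random reader-by-patient term, to both the main model and the fallback.
2. State how replicate is nested and define the indices i and k.
3. Take σ_W, and hence wCV, from the replicate-to-replicate residual.
4. Count reader plus reader-by-patient as the inter-reader component.
5. If the model does not converge, estimate σ_W as the square root of half the mean squared first-minus-second-read difference in the re-read patients.

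The cost is one model term and a few lines of SAP text. No further reads or patients are needed: 20 patients × 3 readers already give about 60 replicate pairs per part.

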#### Effect size

The primary efficacy is based on qualitative parameters, but no exact estimates are available from previous studies due to the use of DWI in this study. A study investigating a manganese-based contrast agent with T1 / T2 and DWI comparing also unenhanced versus CMRI [39] reported qualitative score results on a scale from 1 to 5. These results are used to derive estimates for mean and standard deviation (SD) and scaled down for the 1 to 4 scale used in this study. Calculating an average score per patient and averaging readers after rescaling, leads to averages of 2.3 for unenhanced versus 2.6 for CMRI. This is a difference of 0.3 with each sample's standard deviation of ~1.9, or ~1.5 after rescaling. For estimation of the SD of the samples' differences, a high correlation (0.8) is assumed, which results in 0.95.

[figure not shown]
Conservatively assuming no effect of the subpopulation of the HCC patients (20% of the study population), the effect is  $0.3 \times (1-0.2) = 0.24$ .

Sample size calculation was performed using SAS® version 9.4 resulting in 167 patients needed for analysis (Table 11, Figure 2). Assuming, that only 85% of the image sets will be completely evaluable (all enhanced and unenhanced liver MRI images) and that no patients will drop out (since the efficacy procedure is completed within a few hours for each patient), 197 patients need to be included in the study.

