9.3 Sample Size Considerations

The primary endpoint analysis consists of two co-primary one-sided t-tests at the conventional one-sided significance level of 0.025. Following the FDA's draft guidance on multiple endpoints in clinical studies, adjustment of the type-I-error is not necessary since both primary variables need to show superiority simultaneously. Nonetheless, this affects the type-II-error. To counteract the inflation of the type-II-error, each test's power is set to 0.9 to achieve a study power of at least $0.9 \times 0.9 = 0.81$.

Effect size

The primary efficacy is based on qualitative parameters. When designing the ASC-Man-P016 study, a conservative approach was applied when calculating the sample size due to uncertainties regarding the assumed treatment effect overall and in patients with HCC lesions in particular, and the impact of using diffusion-weighted imaging (DWI).

The original sample size determination was based on a study investigating a manganese-based contrast agent with T1 / T2-weighted imaging and DWI. Efficacy was evaluated by comparison of unenhanced versus CMRI qualitative score results for “likelihood that a lesion represented a metastasis” on a scale from 1 to 5 [1]. These results were used to derive estimates for mean and standard deviation (SD) and scaled down for the 1 to 4 scale used in this study. Calculating a mean score per patient and averaging readers after rescaling, lead to averages of 2.3 for unenhanced versus 2.6 for CMRI. This is a difference of 0.3 with each sample’s standard deviation of ~1.9, or ~1.5 after rescaling. For estimation of the SD of the samples’ differences, a high correlation (0.8) was assumed, which resulted in SD of differences of 0.95.

Conservatively assuming no effect of the subpopulation of the HCC patients (20% of the study population), the difference in the full population was estimated to $0.3 \times (1-0.2) = 0.24$.

This resulted in a need of 167 patients for the analysis to reach 90% power for each test. With an assumption that only 85% of the image sets would be evaluable (all mangoral-enhanced and unenhanced MRI images) and that no patients would drop out (since the MRI procedures are completed within a few hours for each patient), it was concluded that 197 enrolled patients were required as per the original sample size estimation.

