11.2.2 Visualization of focal liver lesions

Visualization of focal liver lesions will be measured by the two variables 'lesion border delineation' (BD) and 'lesion contrast compared to liver background' (LC). Both variables will be determined by qualitative assessment on the following 4-point scales for up to 15 lesions per patient as defined in Section 6.2.3.1 of the protocol: 1='poor', 2='partial / moderate', 3='good', 4='excellent'.

For each reader, the two sum scores (sBD and sLC) are determined for each patient by summarizing the individual scores over all lesions detected by treatment groups UnMRI (unenhanced MRI), MeMRI (mangoral-enhanced MRI) and CMRI (combined mangoral-enhanced MRI plus unenhanced MRI). Both scores are weighted by the number of lesions per patient. Mean difference (sum score weighted by number of matched lesions) will also be derived for matched lesions: Unenhanced MRI vs. Combined MRI and Unenhanced MRI vs. Enhanced MRI.

The handling of MRI scans with more than 15 lesions is described in specific documents (MRI manual for training the investigators on MRI reading procedures and rules and Independent Review Charter) prepared for the independent reading process. If there are more than 15 lesions, the reader will start counting starting from the smallest lesion to the largest lesion and will stop at 15 lesions.

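### The intra-reader coefficient of variation divides reader error by the mean of a 1–4 score, so it falls as the mean rises even when reader error is unchanged

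*SAP*

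**What the plan says.** SAP 13.7.2 plans repeat reads, "assuming repeated assessments per patient (for approximately 20 patients) by three independent readers", and states that "an intra-reader reproducibility will be evaluated separately for readings of MRIs in parts I, II and III". Linear mixed models are fitted to patient-level mean scores for border delineation (BD) and lesion contrast (LC), and they split the variability into intra-reader and inter-reader components.

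The intra-reader component is then expressed relative to the mean: "As a relative measure of reproducibility, the intra-reader coefficient of variation (wCV) defined as" σ_W/μ, where μ "is taken as the mean of true value". SAP 11.2.2 fixes the scale as "1='poor', 2='partial / moderate', 3='good', 4='excellent".

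The wCV does not stand alone. The same section defines the variance σ_W² and an intraclass correlation (ICC). It also plans Bland–Altman plots with 95% limits of agreement, including plots of first against second read for each reader and MRI type. Under SAP 10.2, tests other than the primary analysis are exploratory. The text does not commit to tabulating σ_W, or a confidence interval for it, by part.

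**The concern.** A coefficient of variation has a stable meaning only where zero means none of the quantity. Here the lowest category is labelled 1 by convention. SAP 10.0 allows ordinal ratings to be treated as continuous, which can support means and differences but does not make a ratio to the mean meaningful.

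The direction matters as well. The trial's alternative hypothesis is a higher mean score on combined MRI (Part II) than on unenhanced MRI (Part I). If that is true, the denominator is larger in Part II and its wCV is pulled down without any change in how consistently readers score. With one wCV per part and no caution in the text, a side-by-side table could be taken to show that combined reads are more repeatable.

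**Working it through.** **Inputs**
- Metric: wCV = σ_W/μ, by part (SAP 13.7.2).
- Mean scores: the protocol's sample-size section (8.1.14, effect size) "leads to averages of 2.3 for unenhanced versus 2.6 for CMRI". SAP 9.3 says these derive from "qualitative score results for “likelihood that a lesion represented a metastasis” on a scale from 1 to 5", so they stand in for BD and LC means and were not measured on them.
- σ_W: not given in the documents. Assumption: equal in Parts I and II, range 0.2 to 0.5 score points. Equality is relaxed in step 4.
- Repeat reads: about 20 patients × 3 readers × 1 degree of freedom per pair of reads = about 60 degrees of freedom per part.

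The documents state no wCV, no σ_W and no reproducibility target, so there is no planned figure to reproduce.

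**Step 1. Equal reader error.** wCV_II/wCV_I = (σ_W,II/σ_W,I) × (μ_I/μ_II). With equal σ_W this is 2.3/2.6 = 0.885, so the Part II value is 11.5% lower. σ_W cancels, so the relative change does not depend on its assumed value. The wCVs themselves do:

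| σ_W, both parts (assumed) | wCV Part I | wCV Part II | 1.96 × √2 × σ_W, both parts |
|---|---|---|---|
| 0.2 | 8.7% | 7.7% | 0.55 points |
| 0.3 | 13.0% | 11.5% | 0.83 points |
| 0.4 | 17.4% | 15.4% | 1.11 points |
| 0.5 | 21.7% | 19.2% | 1.39 points |

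The last column, in score points, is identical for the two parts, as it should be when the error is identical.

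**Step 2. Other gains in the mean.** With the protocol's diluted difference of 0.24, 2.3/2.54 = 0.906, which is 9.4% lower. If the SAP's 0.42 is read as score points (an assumption, since it is stated only as an effect size), 2.3/2.72 = 0.846, which is 15.4% lower. No planning mean is given for Part III, so the shift there cannot be sized.

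**Step 3. Dependence on coding.** Same data, same error, different category numbers:
- Coded 1–4: 2.3/2.6 = 0.885, so Part II looks 11.5% better.
- Coded 0–3: 1.3/1.6 = 0.8125, so Part II looks 18.8% better.
- Reversed (5 minus score, means 2.7 and 2.4): 2.7/2.4 = 1.125, so Part II looks 12.5% worse.

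The plan fixes the coding at 1–4. The other two rows only show that the size and even the sign of the comparison come from the labels.

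**Step 4. Unequal reader error.** With a Part II/Part I SD ratio of 0.8, the wCV ratio is 0.8 × 0.885 = 0.71. With an SD ratio of 1.2 it is 1.06, and Part II looks worse. The two wCVs are equal when Part II error is 2.6/2.3 = 1.13 times Part I error, that is 13% higher.

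**Step 5. Against sampling noise.** With 60 degrees of freedom in each part and equal true σ_W, the estimated SD ratio has a 95% range of about 0.77 to 1.29 (from the F distribution with 60 and 60 degrees of freedom). The 11.5% shift lies inside that range. It is directional, however. Holding the means at 2.3 and 2.6 and treating the two SD estimates as independent, Part II would have the lower wCV in about 83% of trials, where 50% would be expected of a neutral measure.

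**The case against.** The strongest reply is that the plan already shows intra-reader error in score units. The Bland–Altman limits for first against second read, by reader and MRI type, are not distorted by a shift in the mean. Absent a systematic shift between reads, their half-width is in essence the repeatability coefficient. This stands as real mitigation. It does not repair the wCV, and the SAP describes these plots as graphical output. Table layouts are in separate shells that are not available here, so σ_W may be tabulated, but the SAP text does not require it.

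The ICC helps less. As defined, inter-reader over total variability, it rises with disagreement between readers and does not measure repeatability.

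It is also fair to say that little depends on the wCV. It is not in the success rule of SAP 13.7.1, reader reproducibility is not a study objective, and the shift is smaller than chance variation with about 20 repeat-read patients. All of this stands and limits the importance of the point.

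Two stronger readings are tempting, and the documents support neither:
- A reader might infer that any lower wCV in Part II would arise only from the higher mean. That holds only if σ_W is equal across parts. σ_W is not given and may differ, for example through compression near the top of the scale.
- A reader might infer that the plan will credit mangoral with better reader consistency. No test, threshold or stated comparison of wCV between parts is planned, so the risk lies in how the values are read side by side.

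**Conclusion.** The point holds in a limited form. The wCV is a poor measure for a score without a true zero, because it changes with the coding and falls as the mean rises at constant reader error. Under the planning means the fall from Part I to Part II is 11.5%, or 9.4% to 15.4% under the other gains considered. These percentages assume equal σ_W in both parts and planning means borrowed from a different kind of score, so they illustrate the mechanism and do not forecast the result. The consequence is confined to an exploratory reproducibility summary. It is a minor point and does not affect the primary analysis.

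**What to change.** In SAP 13.7.2, make the reported intra-reader measure σ_W together with the repeatability coefficient, 1.96 × √2 × σ_W. Give both in score points with 95% confidence intervals, for each of Parts I, II and III and for BD and LC separately. Drop the wCV or, if it is kept, state that it must not be compared across parts.

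The interval is worth having. With about 60 degrees of freedom it runs from about 0.85 to 1.22 times the estimate, so an assumed σ_W of 0.4 would carry limits of about 0.34 to 0.49.

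The cost is SAP wording and a table change. The planned model already yields σ_W, and no new reads are needed. Protocol 8.1.4 leaves the model details to the SAP and does not mention the wCV, so a protocol amendment appears unnecessary. The downside is that one relative summary is lost or qualified.

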Duration of adverse events	
Duration of adverse events will be calculated based on the imputed values for adverse event start date/time and stop date/time.
 
If the duration of the adverse event could not be calculated due to unknown date information, the following assessment to categories will be used:
 
 If the adverse event is marked as "ongoing" in the CRF or the end date is missing, the duration will be categorized as "ongoing". Otherwise, the duration category will be set to "missing".
Flagging of laboratory parameters	Continuous parameters will be classified as low , normal , or high based on reference (normal) ranges. In addition, laboratory parameters are flagged also according to CTCAE grading (G) as G1, G2, G3, or G4
Reproducibility	A consistency of results obtained when the same imaging is performed at short intervals on the same patients using different methods and by different readers.
QTcB interval (msec)	$\text{QTcB interval (msec)} = \frac{\text{QT interval (msec)}}{(\text{RR interval (sec)})^{1/2}}$

Variable / Term	Definition / Way of calculation
QTcF interval (msec)	$\text{QTcF interval (msec)} = \frac{\text{QT interval (msec)}}{(\text{RR interval (sec)})^{1/3}}$

The raw datasets will be in the Study Data Tabulation Model (SDTM) and the analysis datasets will be in the Analysis Data Model (ADaM), where ADaM datasets are derived from SDTM datasets. Throughout the entire study only one CDISC version will be used, there will be no change even if a higher version is available.

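### The SAP's reader ICC puts reader variance in the numerator, so as written it does not measure agreement between readers

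*SAP*

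**What the plan says.** Protocol section 8.1.4 asks for intra- and inter-reader reproducibility from mixed models on the mean border delineation (BD) and lesion contrast (LC) scores, with patients as a random effect. It leaves the details to the SAP and gives no ICC formula.

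SAP section 13.7.2 supplies the details:

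- **Data:** "assuming repeated assessments per patient (for approximately 20 patients) by three independent readers". The Bland-Altman text adds that for these patients "BD and LC will be assessed twice by each reader and MRI type".
- **Model:** "Basically, the model will include reader, patient and replicate as a random effects and divide the total variability into an intra- and inter-reader component". No reader-by-patient term is named.
- **Components:** "Considering reader as a random effect, this model is used to express the observed value as the true value plus the intra-reader error". The variance of the true value, var(μ_i), is labelled inter-reader and var(e_ik) intra-reader. The index i is not defined.
- **ICC:** "The Intraclass Correlation Coefficient (ICC) will also be derived as the inter-reader variability divided by the total variability".
- **Fallback:** "in case this model does not converge we will have patient as a fixed effect instead".

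Table 7 in SAP section 11.2.1 defines reproducibility as consistency of results "on the same patients using different methods and by different readers".

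**The concern.** An agreement ICC asks how much of the total variation comes from real differences between patients, so patient variance belongs in the numerator and reader variance counts against agreement. The SAP sentence does the reverse: its index is lowest when different readers give consistent results on the same patients, which is the property Table 7 sets out to describe.

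Two further gaps sit beside it. Without a reader-by-patient term, disagreement that varies from patient to patient falls mostly into the residual, which the SAP calls intra-reader. And the fallback with patient fixed removes the patient variance that an agreement ICC needs.

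Efficacy rests on subjective 4-point scores and a two-of-three reader rule, and the ICC is the only single-number summary of between-reader agreement that the SAP names. A value near 0 from readers who agree well would make the reads look unreliable, and a high value produced by systematic offsets would look like good agreement.

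**Working it through.** The documents give no variance components and no target ICC, so there is no planned figure to reproduce. All variances below are assumptions; the design (about 20 patients, 3 readers, 2 reads) is from SAP section 13.7.2.

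Notation: P = var(patient), R = var(reader), RP = var(reader × patient), E = residual. Replicate variance is taken as 0. Total = P + R + RP + E.

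- SAP ICC, read literally = R / Total
- Conventional inter-reader agreement ICC = P / Total

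**Step 1. Population values, P = 0.50, E = 0.20**

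| Disagreement | R | RP | Total | SAP ICC | Agreement ICC |
|---|---|---|---|---|---|
| None | 0 | 0 | 0.70 | 0/0.70 = 0.00 | 0.50/0.70 = 0.71 |
| Offsets, moderate | 0.10 | 0 | 0.80 | 0.10/0.80 = 0.13 | 0.50/0.80 = 0.63 |
| Offsets, large | 0.50 | 0 | 1.20 | 0.50/1.20 = 0.42 | 0.50/1.20 = 0.42 |
| Patient-specific, moderate | 0 | 0.15 | 0.85 | 0/0.85 = 0.00 | 0.50/0.85 = 0.59 |
| Patient-specific, large | 0 | 0.50 | 1.20 | 0/1.20 = 0.00 | 0.50/1.20 = 0.42 |

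**Step 2. Estimates from the planned design.** Simulation of 20 × 3 × 2 balanced data, 4,000 runs, additive model as the SAP names it, expected mean squares, P = 0.50, E = 0.20. Median SAP ICC (2.5th to 97.5th percentile):

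- no reader disagreement: 0.000 (0.00 to 0.02)
- RP = 0.50: 0.005 (0.00 to 0.08)

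The two situations cannot be told apart. A separate check by restricted maximum likelihood, with patient SD 0.6 and residual SD 0.3, gave the same picture: mean SAP ICC 0.002 with no disagreement and 0.024 with a reader-by-patient SD of 1.0. The conventional population values there are 0.800 and 0.248.

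**Step 3. The omitted reader-by-patient term.** With 20 patients the interaction has 19 × 2 = 38 degrees of freedom, and the additive model's residual has 120 − 1 − 19 − 2 − 1 = 97. The expected share of RP is:

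- in the reader component: (2 − 2 × 38/97)/(2 × 20) = 0.030
- in the residual: 2 × 38/97 = 0.78

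Take P = 0.50, R = 0.02, RP = 0.15, E = 0.05, so Total = 0.72. The expected residual of the additive model is 0.05 + 0.78 × 0.15 = 0.167 instead of 0.05. The intra-reader SD behind the wCV is therefore inflated by about √(0.167/0.05) = 1.8. Simulated medians for this scenario:

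| Index | True value | Median (2.5th to 97.5th percentile) |
|---|---|---|
| SAP ICC as written | 0.02/0.72 = 0.028 | 0.02 (0.00 to 0.14) |
| Inter-reader ICC, term fitted | 0.50/0.72 = 0.694 | 0.69 (0.44 to 0.83) |
| Intra-reader ICC, term fitted | 0.67/0.72 = 0.931 | 0.93 (0.87 to 0.96) |
| Intra-reader ICC, term omitted | 0.931 | 0.76 (0.57 to 0.87) |

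**Step 4. The fallback.** With patient fixed, the literal ratio becomes R/(R + residual). It is still 0 without offsets. With offset SD 0.5 and residual SD 0.3 it is 0.25/(0.25 + 0.09) = 0.735, so it reads higher as readers drift apart.

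**The case against.** The strongest counter-argument is that the literal reading is not the only one. The SAP calls μ_i the true value, treats e_ik as error around it, and describes the approach as patient-level; the protocol names patients as the random effect. If i indexes patients, var(μ_i)/total is the ordinary ICC and only the label is wrong. That is a fair reading. But the SAP introduces the expression by naming reader as the random effect and labels both the component and the ICC numerator inter-reader, so a programmer following the text would use reader variance.

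The denominator is also open. If total means reader plus residual only, the ratio is still 0 without offsets. If everything outside the residual counts as the inter component, the Step 1 inputs give 0.50/0.70 = 0.71 with no disagreement and 0.60/0.80 = 0.75 or 1.00/1.20 = 0.83 with offsets. That avoids the 0 but still rises with disagreement, so it is not an inter-reader agreement index either.

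Three points limit the finding and stand:

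- All variances are assumed. The exact figures depend on them; the zero without offsets does not.
- The consequence is small. SAP section 10.2 makes everything outside the primary analysis exploratory, the ICC enters no success rule in section 13.7.1, and the planned Bland-Altman displays ("For each MRI type, plots will be done for each pairwise comparison") would show both offsets and scatter directly.
- The 0.44 to 0.83 range applies if only the 20 twice-read patients are used. All patients are read by all three readers, and with single reads of 59 patients the range narrows to about 0.56 to 0.79.

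**Conclusion.** The concern holds. As written, the ICC is a measure of systematic reader offsets relative to total variance. It is 0 for readers without offsets and near 0 for readers with large patient-specific disagreement, and it rises as readers drift apart. Under the assumed variances, one agreement level (0.42) maps to a SAP ICC of either 0.42 or 0.00.

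This rests on reading the inter-reader component as reader variance. If a patient-based ICC was intended, the error is one of labelling, but the missing reader-by-patient term and the patient-fixed fallback remain problems. The ICC does not enter the wCV or the Bland-Altman plots, although the missing term does inflate the wCV. The primary test and the two-of-three rule are unaffected. It should be corrected before analysis, but it does not threaten the trial's main conclusion.

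**What to change.** In SAP section 13.7.2:

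1. State that μ_i is the patient's true score and define the indices.
2. Add a random reader-by-patient term. It can be separated from the residual because about 20 patients are read twice by each reader.
3. For BD and LC, and for Parts I, II and III separately, define inter-reader ICC = P/Total and intra-reader ICC = (P + R + RP)/Total, with Total = P + R + RP + E, plus replicate variance if that term is kept.
4. Replace the fallback. Keep patient random and take var(reader) from [MS(reader) − MS(reader × patient)]/(patients × reads), set to 0 if negative (this form needs balanced data). Alternatively, report a consistency ICC = P/(P + RP + E), labelled as such.
5. Say which patients inform the inter-reader ICC: all patients in the analysis or only those read twice.

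Items 1 and 3 are the essential correction. The cost is a few sentences and one variance term, with no new reads. The estimates will be imprecise if only about 20 patients are used, so report confidence intervals with the ICCs.
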